#### 7.7 Dose Escalation Rule

Please refer to Section 16 for specifics of dose-finding algorithm.

#### 7.8 Phase II Treatment Schedule

| Agent               | Dose             | Schedule            |
|---------------------|------------------|---------------------|
| Anetumab ravtansine | MTD from Phase I | IV D1 every 3 weeks |
| Atezolizumab        | 1200 mg          | IV D1 every 3 weeks |

### 8.0 Dosage Modification Based on Adverse Events

Strictly follow the modifications in this table until individual treatment tolerance can be ascertained. If multiple adverse events are seen, administer dose based on greatest reduction required for any single adverse event observed. Dose modifications apply to the treatment given in the preceding cycle and are based on adverse events observed since the prior dose.

In the event that individual patients experience Grade 3 or Grade 4 treatment related toxicity or intolerable Grade 2 toxicity despite optimal supportive care, treatment might be delayed and/or dose reduced as described below. In the event of multiple toxicities, dose modification should be based on the worst toxicity observed. Subjects are to be instructed to notify Investigators at the first occurrence of any adverse symptom. Decisions on dose reduction and resumption of treatment determined according to the judgment of the investigator.

The start of a new cycle may be delayed by up to 12 weeks due to study treatment-related toxicities. In the event that a cycle has to be delayed by more than 2 weeks due to toxicity, the patient will be taken off study treatment unless otherwise specified below. Note: Patients can continue with Atezolizumab if removed from anetumab ravtansine and remain on study.

#### 8.1 Dose Adjustment and Management Recommendation of anetumab ravtansine

For all TEAEs except for the corneal epitheliopathy and BCVA changes, CTCAE v.4.03 will be used to assess severity.

For TEAEs representing corneal epitheliopathy and BCVA changes, the Bayer Severity

Grading system will be used to assess severity of TEAEs.

TEAEs requiring anetumab ravtansine treatment modification (temporary treatment interruption, dose reduction, or permanent discontinuation of treatment) will be defined as any of the events described below that are possibly, probably, or definitely related to anetumab ravtansine.

#### 8.11 Hematological TEAEs requiring treatment modification

- ANC  $<500/\text{mm}^3$  (CTCAE Grade 4) for  $\geq 7$  days
- Febrile neutropenia (ANC  $<1000/\text{mm}^3$  and a single body temperature reading of  $>38.3^\circ\text{C}$  ( $\geq 101^\circ\text{F}$ ) or a sustained body temperature of  $\geq 38.0^\circ\text{C}$  ( $\geq 100.4^\circ\text{F}$ ) for more than 1 hour
- Platelet count  $<25,000/\text{mm}^3$  (CTCAE Grade 4) for  $\geq 7$  days regardless of the presence of active bleeding or platelet count  $> 50,000/\text{mm}^3$  (CTCAE Grade  $\geq 3$ ) with clinically significant bleeding (i.e., bleeding requiring platelet transfusion)

#### 8.12 Nonhematological TEAEs requiring treatment modification of any or all agents of study treatment

- CTCAE Grade 4 non-hematologic toxicity
- CTCAE Grade 3 non-hematologic toxicity that, in the investigator's opinion, warrants treatment modification excluding the following:
  - CTCAE Grade 3 nausea, vomiting, or diarrhea if manageable with antiemetic or antidiarrheal agents within 7 days would not require treatment modification
  - CTCAE Grade 3 fatigue lasting  $\leq 72$  hours would not require treatment modification
  - Certain asymptomatic CTCAE Grade 3 laboratory abnormalities without a clear clinical correlate, if the investigator determines that this TEAE would not require treatment modification.
  - Grade 3 corneal epitheliopathy according to the Bayer Severity Grading that, in the investigator's opinion, warrant treatment modification.
- Grade 2 corneal epitheliopathy according to the Bayer Severity Grading that, in the investigator's opinion, warrants treatment modification.
- CTCAE Grade  $\geq 2$  neurotoxicity
- AST and/or ALT increase  $> 3.0 \times \text{ULN}$  (CTCAE Grade  $\geq 2$ ) with concomitant increase in total bilirubin  $> 1.5 \times \text{ULN}$  (CTCAE Grade  $\geq 2$ ). For patients with liver metastases, AST/ALT increase  $> 5.0 \times \text{ULN}$  with concomitant increase in total bilirubin  $> 2.0 \times \text{ULN}$

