#### 7.6 Definition of DLT

Dose-limiting toxicity (DLT) will be defined as an AE occurring in Cycle 1 of the study, attributed (definitely, probably, or possibly) to treatment and meeting the following criteria:

- Grade 4 ANC  $\geq 7$  days or  $\geq$ Grade 3 ANC of any duration with fever  $> 38.3^{\circ}\text{C}$ .
- Grade 4 platelet count or Grade 3 platelet count associated with bleeding.
- AST/ALT/ alkaline phosphatase  $\geq$  Grade 3 if total bilirubin  $< 1.5 \times \text{UNL}$ .
- AST/ALT/alkaline phosphatase  $\geq 2.5 \times \text{UNL}$  together with  $\geq$  Grade 2 total bilirubin ( $> 1.5 \times \text{UNL}$ ).
- Other  $\geq$  Grade 3 non-hematologic toxicities (except transient asymptomatic electrolyte abnormality and nausea, vomiting or diarrhea untreated with anti-emetic support or anti-diarrheal agents, respectively).

Grade 3 laboratory abnormalities without clinically significant sequel (e.g., amylase elevation, etc) will NOT be considered DLT.

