|                            |                           | Grade 2   | 
Hold atezolizumab.
 
Initiate symptomatic treatment.
 
Patient referral to GI specialist is recommended.
 
For recurrent events or events that persist <math>> 5</math> days, initiate treatment with 1-2 mg/kg/day oral prednisone or equivalent.
 
Resume atezolizumab if event resolves to grade 1 or better within 12 weeks. If event resolves to grade 1 or better within 12 weeks, taper corticosteroids and resume atezolizumab according to the guidelines above.
 
Permanently discontinue atezolizumab and contact Medical Monitor if event does not resolve to grade 1 or better within 12 weeks. Resumption of atezolizumab may be considered in patients who are deriving benefit and have fully recovered from the immune-related event.
 |
|                            |                           | Grade 3   | 
Hold atezolizumab.
 
Refer patient to GI specialist for evaluation and confirmatory biopsy.
 
Initiate treatment with 1-2 mg/kg/day intravenous methylprednisolone or equivalent and convert to 1-2 mg/kg/day oral prednisone or equivalent upon
   |

| CTCAE SOC | Adverse Event                 | Grade        | Dose Adjustment and Management Recommendations  |
|-----------|-------------------------------|--------------|---|
|           |                               |              | 
improvement.
                     If event resolves to grade 1 or better within 12 weeks, taper corticosteroids and resume atezolizumab according to the guidelines above.
                     Permanently discontinue atezolizumab and contact Medical Monitor if event does not resolve to Grade 1 or better within 12 weeks. Resumption of atezolizumab may be considered in patients who are deriving benefit and have fully recovered from the immune-related event.
   |

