|                                    |   |                             | 
benefit
 
Refer patient to GI specialist.
 
Initiate treatment with 1-2 mg/kg/day intravenous methylprednisolone or equivalent and convert to 1-2 mg/kg/day oral prednisone or equivalent upon improvement.
 
If event does not improve within 48 hours after initiating corticosteroids, consider adding an immunosuppressive agent.
 
If event resolves to grade 1 or better, taper corticosteroids over 1 month.
  |
| Infections and infestations | Meningitis or encephalitis                | All grades                  | 
Permanently discontinue atezolizumab and contact Medical Monitor. Patient may not resume treatment, regardless of benefit.
 
Refer patient to neurologist.
 
Initiate treatment with 1-2 mg/kg/day IV methylprednisolone or equivalent and convert to 1-2 mg/kg/day oral prednisone or equivalent upon improvement.
 
If event resolves to grade 1 or better, taper corticosteroids over <math>\geq 1</math> month. If event does not improve within 48 hours after initiating corticosteroids, consider adding an immunosuppressive agent.
 |
| Investigations              | Lipase increase or serum amylase increase | Grade 1
>ULN - 1.5 x ULN | 
Continue atezolizumab.
 
Monitor amylase and lipase prior to dosing.
  |
|                                    |   | Grade 2 (>1.5 - 2.0 x ULN)  | 
Continue atezolizumab.
 
Monitor amylase and lipase weekly.
   |

| CTCAE SOC                                 | Adverse Event  | Grade  | Dose Adjustment and Management Recommendations   |
|---|--|--|--|
|   |  | Grade 3 (>2.0 - 5.0 x ULN) or 4 (>5.0 x ULN) | 
Hold atezolizumab.
 
Refer patient to gastrointestinal (GI) specialist. Monitor amylase and lipase every other day.
 
If no improvement, consider treatment with 1-2 mg/kg/day oral prednisone or equivalent.
 
Resume atezolizumab if event resolves to grade 1 or better within 12 weeks.
 
Permanently discontinue atezolizumab and contact Medical Monitor if event does not resolve to grade 1 or better within 12 weeks.
 
For recurrent events associated with pancreatitis symptoms, permanently discontinue atezolizumab and contact Medical Monitor. Treatment for recurrent events not associated with pancreatitis symptoms may be resumed after consultation with the trial Principal Investigator.
 |

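### The heading of 8.12 reaches all study agents although its parent 8.1 covers anetumab ravtansine only; read literally, its Grade 3 diarrhea exception contradicts the atezolizumab hold in 8.226

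*Combined protocol and SAP*

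**What the plan says.** Section 8.1 is titled for anetumab ravtansine. Its lead-in defines "TEAEs requiring anetumab ravtansine treatment modification (temporary treatment interruption, dose reduction, or permanent discontinuation of treatment" and limits the events listed below it to those at least possibly related to that drug. Subsection 8.12 then carries the heading "Nonhematological TEAEs requiring treatment modification of any or all agents of study treatment".

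Two of the exceptions under that heading matter here:

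- Gastrointestinal: "CTCAE Grade 3 nausea, vomiting, or diarrhea if manageable with antiemetic or antidiarrheal agents within 7 days would not require treatment modification".
- Laboratory: "Certain asymptomatic CTCAE Grade 3 laboratory abnormalities without a clear clinical correlate, if the investigator determines that this TEAE would not require treatment modification".

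Atezolizumab has its own section, 8.2. In the 8.226 table, the Grade 3 row for diarrhea or enterocolitis says to hold atezolizumab, then "Refer patient to GI specialist for evaluation and confirmatory biopsy", and to start intravenous methylprednisolone. The Grade 3 or 4 row for lipase or amylase increase says to hold atezolizumab, then "Refer patient to gastrointestinal (GI) specialist. Monitor amylase and lipase every other day". The Grade 3 or 4 hyperglycemia row also holds it. None of the three rows exempts manageable or asymptomatic cases.

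Section 8.0 opens with "Strictly follow the modifications in this table until individual treatment tolerance can be ascertained", without saying which table is meant. It also leaves decisions on dose reduction and resumption to the investigator's judgment.

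**The concern.** A dose-modification section is used at the point of care, often by looking up a single subsection. A site that opens 8.12 and believes its heading learns that manageable Grade 3 diarrhea calls for no change to any study agent. A site that opens 8.226 learns that atezolizumab is to be held for the same event.

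The overlap is realistic. Diarrhea is listed for anetumab ravtansine in 15.17 (52.6%) and among the common toxicities of atezolizumab in 15.27, so one episode can reasonably be attributed to both drugs. Section 9.3 sets out supportive care for Grade 3 or 4 diarrhea and does not point to the atezolizumab hold, so 8.12 and 9.3 together can look like a complete pathway. What is at stake is giving atezolizumab again through a possible immune colitis; 15.292 warns that diarrhea on this drug can be very severe and lead to colonic perforation.

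**Working it through.** No arithmetic applies; the check is a comparison of texts.

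**Step 1: scope of the heading.** The title and lead-in of 8.1 name anetumab ravtansine only. Among the neighboring subsections, the heading of 8.11 names no agent, and 8.13 and 8.14 are tied to anetumab ravtansine. Only 8.12 adds a phrase that reaches every agent. The heading is therefore wider than the section it belongs to.

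**Step 2: each Grade 3 exception against the 8.226 table, with the heading taken literally.**

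| 8.12 exception | Matching row in 8.226 | Result |
|---|---|---|
| Diarrhea manageable within 7 days | Grade 3 diarrhea or enterocolitis: hold, no carve-out | Direct conflict |
| Certain asymptomatic laboratory abnormalities, if the investigator so determines | Grade 3-4 lipase/amylase: hold; Grade 3-4 hyperglycemia: hold | Conflict only if the investigator uses the exception |
| Nausea or vomiting; fatigue of up to 72 hours; corneal epitheliopathy | No matching Grade 3 hold row | None |

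**Step 3: the diarrhea conflict.** The 8.226 table already holds atezolizumab at Grade 2, so a literal 8.12 would be looser at Grade 3 than the table is at Grade 2. The instruction in 8.0 to apply the greatest reduction addresses several adverse events in one patient. It does not address one event that falls under two rules.

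**Step 4: the laboratory exception.** It covers only some asymptomatic abnormalities and needs an investigator's determination. Amylase is a plausible candidate, because 7.6 uses it as an example: "Grade 3 laboratory abnormalities without clinically significant sequel (e.g., amylase elevation, etc) will NOT be considered DLT". That sentence serves the DLT definition, however, so it is only indirect support. Lipase and amylase are not in the routine chemistry list of 4.1, but glucose is, so the hyperglycemia overlap does not depend on unscheduled tests.

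**Step 5: what the context says about intent.** The 8.1 lead-in governs the list. The actions in 8.16 and 8.17 concern the anetumab ravtansine dose. Section 8.0 treats the agents separately by letting patients stay on atezolizumab after anetumab ravtansine is stopped. Section 8.21 withholds atezolizumab for higher-grade immune-related events. All of this points to anetumab ravtansine alone.

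**Step 6: reach into the statistics.** The DLT criteria in 7.6, the two-stage rule in 16.4 and the adverse event stopping rules in 16.62 are stated on their own terms and do not draw on the 8.12 exceptions.

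**The case against.** The strongest reply is that the scope is already settled. The lead-in of 8.1 is the operative sentence, a sub-heading should not override it, and atezolizumab has a full section of its own. An exception saying that modification is not required does not forbid a hold, so a site that follows 8.226 breaches neither text. The two diarrhea rules also have different targets: 8.12 concerns events at least possibly related to anetumab ravtansine, and 8.22 concerns events that are potentially immune related, with other causes to be evaluated.

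Most of this stands. It shows that the intent can be recovered and that no atezolizumab rule is missing. It does not remove the overlap when one episode is attributed to both drugs, and it asks the site to work out that a heading in the operative safety text is wrong.

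A reader might infer more than the documents support:

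- **That the holds are mandatory.** The row wording is imperative and 8.0 asks for strict adherence, but 8.226 itself describes its content as guidelines and its holds as recommendations. Unqualified is the accurate word.
- **That both exceptions conflict automatically.** Only the diarrhea exception does so on a literal reading; the laboratory one depends on the investigator.
- **That the treatment delay can be counted in days.** Any count needs assumed onset and resolution days, which the documents do not give.

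**Conclusion.** The heading of 8.12 is wrong as written. Read literally, it sets the Grade 3 diarrhea exception against the unqualified atezolizumab hold in 8.226. It leaves a conditional conflict for Grade 3-4 lipase/amylase and Grade 3-4 hyperglycemia. In context, anetumab ravtansine alone was almost certainly intended.

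The point is minor but concerns safety wording, and it is worth correcting because the instruction is operative. Its size cannot be put as a number of patients: the 52.6% in 15.17 is not broken down by grade, and no Grade 3 diarrhea rate is given for either drug. The conclusion assumes only that some site might take the heading at face value for an event attributable to both drugs. It does not bear on sample size, the DLT definition, or the interim and final decision rules.

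**What to change.** Retitle 8.12 as *Nonhematological TEAEs requiring anetumab ravtansine treatment modification*, and add one sentence after the exceptions: *Atezolizumab modification follows Section 8.2 and the 8.226 table regardless of these exceptions.*

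The 8.226 holds and the supportive care in 9.3 can stay as they are. The cost is one heading and one sentence at the next amendment, with no new procedures, visits or patients and no change to any atezolizumab rule.

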#### **Bayer classification and management of corneal epitheliopathy**

| Toxicity (worst grade, worst eye) | Corneal morphology changes   | Anetumab ravtansine interruption and dose reduction   | Remedial eye treatment a  |
|--|---|--|---|
| Grade 0                                  | No pathologic changes   | No change/continue treatment   | Treatment with ophthalmic lubricants b   |
| Grade 1                                  | Treatment-emergent superficial punctate keratitis (SPK) (new or worsening by $\geq 2$ grades) | no change/continue treatment   | Treatment with ophthalmic lubricants should be used. Topical steroids may be added. b                          |
| Grade 2                                  | Epithelial opacities
Corneal microcysts or microdeposits                                   | Treat on time at the same dose if ophthalmological exam can be performed as frequently as prescribed | Intensive treatment with ophthalmic lubricants (may be enhanced with ointments b ). Topical steroids should be |

|  |   |   |  |
|--|---|---|--|
|  | Corneal erosion
Stromal opacity
(non-central)                         | by the investigator.
If ophthalmological exam cannot be performed as frequently as prescribed by the investigator, treatment may be held until the event has resolved to the acceptable severity level. b
The event must resolve to acceptable level within 6 weeks after the last dose. c, d
Treatment may be restarted at the same dose or at the dose reduced by 1 level. b, c                             | added.
Therapeutic contact lenses may be used. b   |
| Grade 3  | Corneal ulcer without risk of acute rupture
Stromal opacity
(central) | Treatment should be held until the event has resolved to the acceptable severity level. b
The event must resolve to acceptable level within 6 weeks after the last dose. c, d
Treatment should be restarted at the dose reduced by 1 level. e
If Grade 3 corneal morphology change occurs again after dose reduction, the current dose should be reduced by 1 level or permanently discontinued. b | Intensive treatment with ophthalmic lubricants, enhanced with ointments. Topical steroids should be added.
Therapeutic contact lenses or eye occlusion are recommended. b  |

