#### **8.17 Anetumab ravtansine dose adjustments in response to neutrophil and platelet nadir counts of the previous cycle:**

| CTCAE System/Organ/Class (SOC)       | GRADE   | ADVERSE EVENT   | AGENT               | ACTION**              |
|--------------------------------------|---------|---|---------------------|-----------------------|
| INVESTIGATIONS                       | Grade 2 | Neutrophil count decrease >500 or <500 for <7 days AND Platelet count decreased $\geq$ 25,000   | Anetumab ravtansine | No change             |
| INVESTIGATIONS                       | Grade   | Neutrophil count decrease <500 for $\geq$ 7 days AND Platelet count decreased <25,000 for $\geq$ 7 days with or without active bleeding, OR <50,000 for $\geq$ 7 days with clinically significant bleeding b | Anetumab ravtansine | Decrease 1 dose level |
| BLOOD AND LYMPHATIC SYSTEM DISORDERS | Grade 3 | Febrile neutropenia AND Platelet count <25,000 for $\geq$ 7 days with or without active bleeding, OR <50,000 for $\geq$ 7 days with clinically significant bleeding b  |                     | Decrease 1 dose level |

a Anetumab ravtansine dose reduction by 1 dose level translates to a change from 6.5 mg/kg (BW) Q21D to 5.5 mg/kg Q21D, or from 5.5 mg/kg Q21D to 4.5 mg/kg Q21D.

b Clinically significant bleeding is that which requires platelet transfusion.

c Febrile neutropenia is defined as ANC < 500 with fever of  $>38.3^{\circ}\text{C}$  [ $101^{\circ}\text{F}$ ] or a sustained body temperature of  $\geq 38.0^{\circ}\text{C}$  [ $100.4^{\circ}\text{F}$ ] for more than one hour).

If anetumab ravtansine treatment modification is required due to a nonhematological TEAE, and the continuation of anetumab ravtansine treatment is appropriate at the investigator's discretion, then the anetumab ravtansine dose will be reduced after CTCAE Grade 4 nonhematologic TEAE and Bayer Grade 3 corneal epitheliopathy, or either reduced or maintained at the investigator's discretion after CTCAE Grade 3 non-hematologic TEAE or Bayer Grade 2 corneal epitheliopathy change (attached table).

The anetumab ravtansine dose reduction due to nonhematological TEAEs will be performed by 1 mg/kg Q21D as appropriate, i.e., from 6.5 mg/kg Q21D to 5.5 mg/kg Q21D, or from 5.5 mg/kg Q21D to 4.5 mg/kg Q21D.

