### **Dose re-escalation**

Dose re-escalation for anetumab ravtansine after dose reduction is not allowed, except reescalation after dose reduction for corneal epitheliopathy if the first Grade 3 event resolves to Grade  $\leq 2$  within 21 days and does not recur.

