### 16.2 Phase I Study Design

The primary endpoint of the phase I portion of this trial is to estimate the MTD of anetumab ravtansine combined with atezolizumab. A standard 3+3 phase I design will be utilized. Three patients will be treated at each dose level and observed for a minimum of three weeks (i.e. one full cycle) before new patients are treated. Doses will not be escalated in any individual patient.

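### Section 8.12 leaves treatment modification after Bayer Grade 3 corneal epitheliopathy to investigator opinion and lists it among exclusions, while the 8.15 table and 8.17 call for a dose reduction

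*Combined protocol and SAP*

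**What the plan says.** Four places in the combined protocol and SAP govern anetumab ravtansine after a corneal event.

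- **Section 8.12** lists the non-hematological events that require treatment modification. One bullet reads "CTCAE Grade 3 non-hematologic toxicity that, in the investigator's opinion, warrants treatment modification excluding the following". Its sub-list covers manageable gastrointestinal events, short-lived fatigue and certain laboratory findings, and then "Grade 3 corneal epitheliopathy according to the Bayer Severity Grading that" the investigator considers to need modification. The milder grade is a separate top-level bullet: "Grade 2 corneal epitheliopathy according to the Bayer Severity Grading that, in the investigator's opinion, warrants treatment modification".
- **The 8.15 table, Grade 3 row**, says "Treatment should be held until the event has resolved to the acceptable severity level", with footnote b (investigator and/or ophthalmologist discretion). A later sentence in that row says treatment should resume one dose level lower. It carries footnote e, which defines the dose steps, and not footnote b.
- **Section 8.17**, in its text on non-hematological events, says the "anetumab ravtansine dose will be reduced after CTCAE Grade 4 nonhematologic TEAE and Bayer Grade 3 corneal epitheliopathy". The same sentence allows the dose to be either lowered or kept, at the investigator's discretion, after CTCAE Grade 3 non-hematologic events or Bayer Grade 2 corneal changes. The rule is conditional on a modification being required and on continuation being appropriate.
- **The withdrawal sentence** that closes this text, just before the Dose re-escalation heading, counts a corneal event as resolved at Bayer Grade 2 or lower.

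**The concern.** Section 10.554 names corneal epitheliopathy an adverse event of special interest and relies on the protocol's own dose-modification schemes to manage it. Those schemes should give one answer for each Bayer grade. For Grade 3 they do not: an investigator starting from 8.12 can conclude that no modification is required, while one starting from the 8.15 table is told to resume at a lower dose. What is at stake is the safety of patients with an ulcer or central stromal opacity, and whether patients assigned the same dose are dosed by the same rule after the same event.

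**Working it through.** No sample size, power or error rate is involved, so the check is a side-by-side reading.

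| Source | Bayer Grade 2 | Bayer Grade 3 |
|---|---|---|
| 8.12 | Top-level trigger, by investigator opinion | Sub-item under the exclusions, by investigator opinion |
| 8.15 table, hold | Treat on time if eye examinations can be done as prescribed; otherwise a hold is optional | Should be held (footnote b: discretion) |
| 8.15 table, restart dose | Same dose or one level lower | Should be one level lower (footnote e: dose steps only) |
| 8.17, dose | Reduced or maintained, by discretion | Will be reduced |

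**Step 1: Grade 2 as a control.** All three sections leave the dose after Grade 2 to the investigator, so they agree.

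**Step 2: Grade 3.** Section 8.12 uses the same opinion wording as for Grade 2, but the table and 8.17 do not offer the choice of keeping the dose. The sections part company at this grade.

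**Step 3: does the nesting matter?** Read literally, 8.12 removes from the required modifications those Grade 3 corneal events that the investigator thinks need one. That undercuts itself and suggests a mis-nested bullet. Suppose it belongs at the top level. Modification is then required only if the investigator thinks so, and the mismatch with the restart sentence and with 8.17 remains.

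**Step 4: how the sections interact.** Section 8.17 begins from the condition that modification is required.
- Nested reading: 8.12 does not require modification, so 8.17 is not reached.
- Promoted reading: 8.17 is reached only if the investigator's opinion is yes.
- Going directly to the 8.15 table: restart is one level lower.

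The same event can thus lead to an unchanged or a reduced dose, depending on the section followed.

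**Step 5: the acceptable level.** The table uses this term for both grades without defining it. The withdrawal sentence gives Bayer Grade 2 or lower, and the Dose re-escalation paragraph uses the same cut-off. That fits a Grade 3 hold. It does not fit a Grade 2 hold, because the event is already within the threshold. Section 8.16 gives CTCAE Grade 1 for restart, but its next sentence, which mentions epitheliopathy, reads as incomplete, so I place no weight on it.

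**Step 6: the lowest dose.** Footnote e and 8.17 define two steps only, 6.5 to 5.5 mg/kg and 5.5 to 4.5 mg/kg. The 7.11 treatment table makes 4.5 mg/kg an assigned dose (level -1). For Grade 3 that recurs after a reduction, the 8.15 table offers permanent discontinuation as an alternative. A first Grade 3 event at 4.5 mg/kg has no stated action.

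**The case against.** The best defence is that 8.12 is a general trigger list and 8.15 is the specific rule. The 8.15 text sends corneal events at least possibly related to the drug to its table and bases decisions only on corneal severity. The exclusion nesting may be a formatting or extraction slip, and the table says should, not must. Much of this is fair, and I do not rely on the nesting. But no sentence gives 8.15 precedence over 8.12, and 8.17 takes its condition from whether modification is required. Section 8.0 does not settle the matter: it asks for strict adherence to the modification table and also leaves dose reduction to investigator judgment.

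Footnote b might also mean that the acceptable level is itself discretionary. If so, the plan should say so and explain how that fits the fixed threshold in the withdrawal sentence.

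Several stronger readings are tempting but not supported:

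- *The hold is mandatory in both the table and 8.17.* Section 8.17 covers only the dose, and the table's hold carries footnote b. Investigator opinion in 8.12 therefore does not contradict the hold; the conflict concerns the dose reduction.
- *A Grade 2 hold is satisfied the moment it starts.* This applies a withdrawal threshold to a term that the table leaves undefined, and the Grade 2 hold is optional. The supported point is the missing definition.
- *The re-escalation exception contradicts 16.2.* The Dose re-escalation paragraph says "Dose re-escalation for anetumab ravtansine after dose reduction is not allowed, except reescalation after dose reduction for corneal epitheliopathy", subject to conditions, while 16.2 says "Doses will not be escalated in any individual patient". Section 16.2 describes the phase I 3+3 design and reads naturally as no escalation above the assigned level. Returning towards that level after a toxicity reduction is a different matter.

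**Conclusion.** The point holds for the Grade 3 dose instruction: 8.12 makes modification a matter of opinion, while the table's restart sentence and 8.17 call for a reduction, and 8.12 can keep 8.17 from being reached. The undefined acceptable level is a second, smaller gap, and the 4.5 mg/kg case is an omission. Together they are an internal inconsistency affecting patient safety and consistent dosing.

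The size cannot be quantified. A reader might apply the earlier study's 11 of 38 patients (29%) with corneal events at 6.5 mg/kg (Section 1.22) to the 37 phase II patients. That would be wrong here. The 11 are corneal events of any severity, and Section 1.22 says that none affected the deep stroma, was considered serious or led to discontinuation. Bayer Grade 3 means an ulcer without risk of acute rupture or a central stromal opacity. The phase II dose is also not yet known, and Section 1.22 expects lower corneal risk at lower exposure. The number affected is the number of Bayer Grade 3 events, for which the documents give no rate.

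Nor do the documents support calling the trial's results uninterpretable. Section 16 plans no dose-intensity or dose-reduction-rate analysis, DLTs have their own definition in 7.6, and the phase II primary endpoint is confirmed response.

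The conclusion assumes that the opinion wording in 8.12 is as printed. It does not depend on the bullet's indentation.

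**What to change.** Reconcile 8.12, the 8.15 table, 8.17 and its closing withdrawal sentence in one edit:

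1. Give one instruction per Bayer grade, worded the same wherever it appears, and say which section governs corneal events.
2. Put the Grade 3 item in 8.12 at its intended list level and make its opinion wording agree with the table and 8.17.
3. Define the acceptable severity level once, so that it works for both the Grade 2 and the Grade 3 rows, or state that it is left to discretion.
4. State what applies when a one-level reduction is called for at 4.5 mg/kg.

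The clinical team decides the content; this review takes no view on which rule is right. The cost is protocol wording only, with no change to sample size, decision rules or planned analyses.
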